No specific data on the non-arteritic AION incidence rate are available for patients with Geographic Atrophy. Based on the limited human exposure and the epidemiological data, the Safety Monitoring Committee (SMC) and the Sponsor concluded that the findings could be coincidental, but a causal relationship to the trial drug cannot be fully excluded. Accordingly, the second SAE was reported as a SUSAR. There were a total of 12 ocular AEs; 4 were considered study drug-related and 5 were considered procedure-related. All ocular AEs, except for the optic ischaemic neuropathies were of mild intensity. All ocular AEs related to study drug or procedure recovered, with the exception of the second AION case.

Overall, 20 systemic AEs were reported. None of these were considered study drug-related and all were of mild or moderate intensity.

No Adverse Events of Special Interest (AESIs), DLEs or deaths were reported, and there was no identifiable exposure/dose-AE relationship. There were no apparent patterns of any clinically significant abnormalities in the general (ECG, vital signs, lab safety parameters) or ophthalmological (IOP, slit lamp, BCVA, SD-OCT, FAF, CFP and OCT-A) safety assessments.

For a more detailed description of BI 754132, please refer to the current IB [[c22785135](#)].

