If DLEs are observed in the first two consecutive patients of a previously untested dose level, subsequent enrolment to that cohort will be stopped. The BLM will be re-run to confirm that the dose level still fulfils the EWOC principle. Based on this information, the SMC will evaluate whether the next patients will be enrolled at the same dose level, or if they will be enrolled at a lower dose level.

As a sensitivity analysis, the BLM might also be run again shortly before the SMC meeting, using all AE data available up to this time point.

The maximum tolerated dose (MTD) is considered as reached if at least 6 patients have been evaluated at a dose level which is the model's recommendation for the next dose cohort. Note that the MTD will likely be the highest feasible dose, 6 mg, rather than the highest tolerable dose in a strict sense. The SMC may decide on stopping the dose escalation after the criterion for MTD is fulfilled. Further patients may be included to confirm that the EWOC criterion is still fulfilled.

In [Figure 3.1: 1](#), the dose escalation process is depicted as planned, i.e., if no DLE occurs in the trial and dose escalation may proceed up to the highest dose level.

[figure not shown]

Figure 3.1: 1 Schematic representation of the dose escalation process in the SRD part

MD part:

The MD part will consist of one dose cohort (6 patients). After the SRD part has been completed, the SMC will decide on the selection of the highest dose (e.g. 6 mg) established as safe and tolerable during the SRD part to be used in the MD part. Patients that had received a dose in the SRD part of the trial (regardless of the eye) will not be included. In the MD part, patients will receive three consecutive dose injections over a 3-month period (dosing every 4 weeks).

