### **3.3.4.3 Discontinuation of the trial by the sponsor**

Boehringer Ingelheim reserves the right to discontinue the trial overall or at a particular trial site at any time for the following reasons:

1. Failure to meet expected enrolment goals overall or at a particular trial site.
2. Emergence of any efficacy/safety information invalidating the earlier positive benefit-risk-assessment that could significantly affect the continuation of the trial.
3. Deviations from GCP, the trial protocol, or the contract impairing the appropriate conduct of the trial.

For the following scenario further enrolment and entering into the trial will be interrupted by the sponsor once the sponsor becomes aware (i.e. stopping rule):

- A single serious adverse reaction (i.e. a single serious adverse event) or two severe adverse reactions in two different patients (regardless of the system organ class) confirmed by both the investigator and sponsor as having a reasonable causal relationship to the IMP administration.
- For the MD part: Occurrence of AION or relevant predisposing changes of the optic disc in the study eye after administration of BI 754132.

The investigator / the trial site will be reimbursed for reasonable expenses incurred in case of trial termination (except in case of the third reason).

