### 7.2 PLANNED ANALYSES

#### 7.2.1 General considerations

##### 7.2.1.1 Dose escalation in the SRD part

The dose escalation will be guided by a Bayesian 2-parameter logistic regression model with overdose control [[R13-4803](#), [R13-4806](#)]. For a given dose, the EWOC criterion is that there should be less than 25% risk that the true ocular and systemic DLE rate is above 0.25. The BLRM will not be used for the analysis of the primary endpoint.

The model is given as follows:

$$\text{logit}(\pi_d) = \log(\alpha) + \beta * \log(d/d^*),$$

where  $\text{logit}(\pi) = \log(\pi/(1-\pi))$ ,  $\pi_d$  represents the probability of having a DLE in the evaluation period at dose  $d$ ,  $d^* = 6$  mg is the reference dose, allowing for the interpretation of  $\alpha$  as the odds of a DLE at dose  $d^*$ , and  $\theta = (\log(\alpha), \log(\beta))$  with  $\alpha, \beta > 0$  is the parameter vector of the model.

The estimated probability of a DLE at each dose level from the model will be summarized using the following intervals:

Target toxicity: [0.00, 0.25]

Over toxicity: [0.25, 1.00]

The BLRM-recommended dose for the next cohort is the dose level with the highest posterior probability of the DLE rate falling in the target interval [0.00, 0.25] among the doses fulfilling EWOC. Thus, it should be unlikely (< 25% posterior probability) that the DLE rate at that dose will exceed 0.25. However, the maximum allowable dose increment for the subsequent cohort will be no more than 233% from the previous dose up to doses of 3 mg, and to a maximum of 100% from the previous dose from dose 3 mg onwards. Dose escalation will continue up to the 6 mg dose as long as the EWOC criterion for the next dose level is fulfilled. At the final dose, at least 6 treated patients are required. However, the SMC may decide to include an additional number of patients at this dose level.

Since a Bayesian approach is applied, a prior distribution  $f(\theta)$  for the unknown parameter vector  $\theta$  needs to be specified. This prior distribution will be specified as a mixture of three multivariate normal distributions, i.e.

$$f(\theta) = a_1 f_1(\theta) + a_2 f_2(\theta) + a_3 f_3(\theta)$$

with  $a_i$ ,  $i = 1, 2, 3$  the prior mixture weights ( $a_1 + a_2 + a_3 = 1$ ), and  $f_i(\theta) = \text{MVN}(\mu_i, \Sigma_i)$ , the multivariate normal distribution of the  $i$ -th component with mean vector  $\mu_i$  and covariance matrix  $\Sigma_i$ , where

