## 10.4 STATISTICAL APPENDIX

A BLRM with overdose control will be used to guide dose escalation in the SRD part of this study. The BLRM is introduced in [Section 7.2](#), which also specifies the prior for the model. After patients in each cohort have completed the evaluation period of 7 days, the prior distribution will be updated through Gibbs sampling procedures with the accumulated DLE data from the evaluation period. Posterior probabilities for the rate of DLEs will be summarised from the BLRM. Selection of the next dose will be based on these probabilities as well as on other safety and laboratory data.

The purpose of this statistical appendix is to present performance metrics (operating characteristics) that illustrate the precision of the design in estimating the MTD (see

Section 3.1) under various dose-toxicity relationships through computer simulation. These results are summarized in [Table 10.4: 3](#). In addition, recommendations of the next dose level by the BLRM with overdose control principle are provided under various hypothetical outcome scenarios, to show how it facilitates on-study dose-escalation decisions (see [Table 10.4: 1](#)). For simplicity reasons, a cohort size of 3 patients who are all evaluable is assumed.

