In scenario 7, there is the first DLE in the first cohort of the 6 mg dose group. Then the dose would have to be reduced to 3 mg for the next cohort. In case of no further DLE, the SRD part of the trial could stop after 18 patients overall (scenarios 7b, 7c).

In contrast, if the first DLE occurs only in the second cohort of dose group 6 mg (scenario 8), then the SRD part of the trial could still be completed with a total of 15 patients. However, if there were 2 DLEs in the highest dose group, then the model would recommend to return to dose 3 mg (scenario 9).

Table 10.4: 1 Hypothetical data scenarios

Scenario	Dose (mg/eye)	# Pat.	# DLE	Current Dose: P(OD)	Next recomm. Dose (mg/eye)	Next dose:	
						P(TD)	P(OD)
1	0.3	3	0	0.015	1	0.960	0.040
2	0.3	3	1	0.309	N/A	N/A	N/A
3	0.3 1	3 3	0 0	0.012	3	0.963	0.064
3b	0.3 1 3 6	3 3 3 6	0 0 0 0	0.013	6	0.987	0.013
4	0.3 1	3 3	0 1	0.202	1	0.798	0.202
4b	0.3 1	3 6	0 1	0.077	1	0.923	0.077
5	0.3 1	3 6	0 2	0.313	0.3	0.894	0.106
5b	0.3 1	6 6	0 2	0.047	1	0.776	0.224
5c	0.3 1	6 9	0 2	0.109	1	0.891	0.109
6	0.3 1 3	3 3 3	0 0 1	0.218	3	0.782	0.218
6b	0.3 1 3	3 3 6	0 0 1	0.088	3	0.912	0.088
7	0.3 1 3 6	3 3 3 3	0 0 0 1	0.253	3	0.960	0.040
7b	0.3 1 3 6	3 3 6 3	0 0 0 1	0.016	6	0.806	0194

Table 10.4: 1 Hypothetical data scenarios (cont'd)

Scenario	Dose (mg/eye)	# Pat.	# DLE	Current Dose: P(OD)	Next recomm. Dose (mg/eye)	Next dose:	
						P(TD)	P(OD)
7c	0.3	3	0	0.085	6	0.915	0.085
	1	3	0				
	3	6	0				
	6	6	1				
8	0.3	3	0	0.113	6	0.887	0.113
	1	3	0				
	3	3	0				
	6	6	1				
9	0.3	3	0	0.364	3	0.944	0.056
	1	3	0				
	3	3	0				
	6	6	2				

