## 7.4 PRIMARY ENDPOINTS

### SRD part:

**Section 5.2.1 of the CTP:** *A dose limiting event (DLE) is defined as the occurrence of any of the following events as ocular DLE (in the study eye):*

- *Development of sterile endophthalmitis and/or sterile inflammation of the vitreous grade 3+ according to Standardization of Uveitis Nomenclature (SUN) working group (WG) grading scheme for anterior chamber cells measured by slit lamp and a duration of 5 or more days*
- *Visual loss of more than 15 letters at any given time point due to treatment effect in the study eye confirmed on consecutive visits*
- *Persistent IOP over 30 mmHg for 3 days*
- *Signs of vascular occlusion in the retina (haemorrhage of the macula would not be included as this is a possible sign of CNV occurrence; peripheral retinal haemorrhage may be a sign of vascular occlusion)*

[...]

or as systemic DLE:

- *Drug-related AEs of moderate and severe intensity according to CTCAE (14) out of the following:*
  - *Self-reporting paraesthesia, dysgeusia, taste abnormality, taste disorder, hyposmia (15)*
  - *Diarrhea, cough (16)*

*Each DLE needs to be reported as AESI.*

Descriptive statistics (number and percentage of patients with ocular (in study eye) and systemic DLEs) will be provided by treatment group and in total, based on the TS.

The results of the final BLRM after completion of the SRD part will be provided based on the TS, and based on the DLE evaluable set in case the DLE evaluable set and the TS differ.

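### Should the final dose-toxicity model in SAP 7.4 also be run with the optic ischaemic neuropathies counted as events?

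*SAP*

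**What the plan says.** Under the primary endpoint for the single rising dose (SRD) part, SAP 7.4 repeats the protocol's DLE list and adds that "The results of the final BLRM after completion of the SRD part will be provided based on the TS". A further run uses the DLE evaluable set if it differs from the treated set. SAP 7 fixes the prior as the one in protocol 7.2.1.1.

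The ocular DLE list has four items: sterile inflammation of a given grade and duration, confirmed treatment-related loss of more than 15 letters, persistently raised intraocular pressure, and signs of vascular occlusion in the retina. The optic nerve is not named.

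Protocol 1.2 reports the SRD outcome: "No Adverse Events of Special Interest (AESIs), DLEs or deaths were reported, and there was no identifiable exposure/dose-AE relationship". It also says: "All ocular AEs related to study drug or procedure recovered, with the exception of the second AION case". It adds that a causal link could not be fully excluded and that the second serious event was reported as a SUSAR.

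Protocol 7.2.1.1 limits the role of the Bayesian logistic regression model (BLRM): "The BLRM will not be used for the analysis of the primary endpoint". For the multiple-dose (MD) part, protocol 3.3.4.3 makes the following a reason to interrupt enrolment: "For the MD part: Occurrence of AION or relevant predisposing changes of the optic disc in the study eye after administration of BI 754132".

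**The concern.** The SAP is dated September 2022, after the February 2022 protocol revision that describes these cases. The sponsor therefore knew of them when 7.4 was finalised. The section still plans one model on an event count of zero and varies only the patient set, never the events.

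The report will then show, under the primary endpoint, an overdose probability of about 0.01 at 6 mg, the dose that SAP 6.1 lists for the MD part. That figure carries no information on the event the sponsor took seriously enough to make an MD enrolment-interruption criterion. A reader who sees it alone could take it as reassurance on all serious ocular harm.

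The protocol offers something like a precedent. Section 3.1 allows an optional check of robustness: "the BLM might also be run again shortly before the SMC meeting, using all AE data available up to this time point". SAP 7.4 has no counterpart for the final model and does not restate the event window. If counting the neuropathies pushed the 6 mg figure past the overdose limit, the omission would hide a material sensitivity.

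**Working it through.** **Inputs**
- Model (protocol 7.2.1.1): logit(π_d) = log α + β·log(d/6), with d in mg.
- Prior on (log α, log β): mixture with weights 0.90, 0.05 and 0.05; means (−2.197, −0.223), (−0.405, −0.514) and (−4.595, −0.259); SDs (2, 1), (2, 1) and (5, 0.01); no correlation.
- Patients (protocol 1.2): 3, 3, 3 and 6 at 0.3, 1, 3 and 6 mg.
- Overdose limit (protocol 7.2.1.1): P(rate above 0.25) must be below 0.25.
- Assumption: the dose and eye of each case are not in the readable text, so every placement of one or two events is shown.

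**Formula**

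The posterior is proportional to the prior times ∏ π_d^y (1 − π_d)^(n − y) over the four doses. At 6 mg, log(d/6) = 0, so π ≥ 0.25 means log α ≥ log(0.25/0.75) = −1.099. The integral was done numerically and split exactly at that threshold.

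**Reproducing the protocol's own figures (Tables 7.2.1.1: 2 and 10.4: 1)**

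| Case | Protocol | Recomputed |
|---|---|---|
| Prior, 6 mg | 0.304 | 0.306 |
| Scenario 3b, no event, 6 mg | 0.013 | 0.012 |
| Scenario 8, one event at 6 mg | 0.113 | 0.111 |
| Scenario 9, two events at 6 mg | 0.364 | 0.367 |
| Scenario 7, 6 mg | 0.253 | 0.256 |
| Scenario 6, 3 mg | 0.218 | 0.207 |

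The largest gap is 0.218 − 0.207 = 0.011. Any result within 0.011 of 0.25 is treated as too close to call.

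**P(rate ≥ 0.25 at 6 mg) if neuropathies were counted**

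One event: 0.053 (at 0.3 mg), 0.063 (1 mg), 0.082 (3 mg), 0.111 (6 mg). All are well below 0.25.

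Two events:

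| Placement | Probability | Against 0.25 |
|---|---|---|
| Both at 6 mg | 0.367 | above |
| 3 and 6 mg | 0.294 | above |
| Both at 3 mg | 0.255 | too close |
| 1 and 6 mg | 0.240 | too close |
| Other six | 0.166 to 0.219 | below |

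The figure at 3 mg with two events is 0.055 to 0.100, below the limit in every placement.

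**Are the cases excluded by definition?** No. A neuropathy with confirmed, treatment-related loss of more than 15 letters in the study eye would be a DLE. The cases are outside the model because none was classed as one.

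**Is the event window open?** No. Protocol 7.2.1.1 defines π_d as the probability of a DLE in the evaluation period, section 3.1 sets that period at 7 days, and the statistical appendix updates the model "with the accumulated DLE data from the evaluation period". The SAP builds on protocol section 7. Extending the window to end of trial would leave the count at zero, because no DLE was reported.

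**Does anything depend on the figure?** All 15 SRD patients had completed by the current amendment, so escalation is over. The Safety Monitoring Committee and sponsor assessed the cases directly. Protocol 1.4.2.6 lists what followed in the MD part: optic disc assessment, sentinel dosing, changed eligibility criteria and updated consent. SAP 7.8.1 tabulates serious, drug-related, drug-related serious and ocular adverse events by treatment, system organ class and preferred term, and adds a listing of ocular symptoms.

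**The case for a change.** The strongest case for a change is that the run is cheap and the answer is not known in advance. One extra fit with the fixed prior would show whether 0.012 is robust. The possible range, up to 0.367, is about 30 times that figure (0.367/0.012 = 30.6) and crosses the limit in some placements. The sponsor holds the missing facts on dose and eye.

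The arithmetic in that argument stands. So does the remark that a reader of 7.4 alone is not told that the neuropathies are uncounted. Three things weaken it as a reason to amend the plan.

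First, the run would count events under a definition written after the cases were known, with a prior calibrated to DLE rates. Statisticians would reasonably disagree on whether the result means anything. The rerun in protocol 3.1 is weak support: it is optional, tied to committee meetings, and does not say that other events would be recounted as DLEs.

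Second, the protocol already prints much of the answer. Table 10.4: 1 gives the 6 mg figure for zero, one and two events at that dose, and its text says what the model recommends "if there were 2 DLEs in the highest dose group".

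Third, a crossing needs two counted study-eye cases at the higher doses, and the readable text does not establish that.

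The difference between the DLE list and the MD enrolment criterion is not a contradiction. One defines the SRD primary endpoint and the other governs enrolment in the MD part. The MD primary endpoint, patients with drug-related adverse events, would capture a neuropathy judged related.

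**Conclusion.** No change to the plan is needed. Followed as written, SAP 7.4 gives a correct posterior for the prespecified event, about 0.012 at 6 mg. That model is not the primary-endpoint analysis and has no escalation decision left to inform. The neuropathies reach the reader through the adverse event tables, where they can be judged as cases rather than through a model built for something else.

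The sensitivity is real but conditional: 0.053 to 0.111 with one case counted and 0.166 to 0.367 with two. It is clearly past 0.25 only with both at 6 mg, or one each at 3 and 6 mg. A reversal at 6 mg is possible but not shown.

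This rests on the reported absence of DLEs, on 3/3/3/6 patients and on the protocol prior. Dose, eye, onset and letter loss of the cases are not in the readable text, and unreadable parts of either document may already address them. A footnote beside the final model, saying that no neuropathy was classed as a DLE and pointing to the adverse event tables, would be a courtesy that the report's authors can add without amending the SAP.

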**MD part:**

Descriptive statistics (number and percentage of patients with drug-related AEs) will be provided, based on the TS.

## **7.5 SECONDARY ENDPOINTS**

### **7.5.1 Key secondary endpoints**

This section is not applicable as no key secondary endpoints have been specified in the protocol.

### **7.5.2 Secondary endpoints**

[figure not shown]
All secondary safety endpoints defined in [Section 5.2.2](#) will be analysed descriptively, based on the TS (refer to TSAP [Section 7.8.1](#) Adverse events for details).

**SRD part:**

The PK endpoints  $C_{max}$ ,  $AUC_{0-\infty}$ , and  $t_{max}$  specified in [Section 5.2.2](#) will be analysed descriptively, based on the PKS. Dose proportionality will be explored descriptively for the PK endpoints  $AUC_{0-\infty}$  and  $C_{max}$  if feasible.

**MD part:**

Systemic exposure of BI 754132 after multiple IVT doses by determination of  $C_{min,1}$  and  $C_{min,2}$  (trough levels before second and third administrations) and serum concentrations 4, 8 and 14 weeks after the third administration will be determined in the MD part along with descriptive statistics, based on the PKS.

## **7.7 EXTENT OF EXPOSURE**

Descriptive statistics are planned for this section of the report based on the TS. The date and time of drug administration will be listed for each patient.

## **7.8 SAFETY ANALYSIS**

All safety analyses will be performed on the TS.

If not stated otherwise, the safety results will be sorted by treatment group.

The safety data for treated patients who failed to complete the study (dropouts or withdrawals) will be reported as far as their data are available. All withdrawals will be documented and the reason for withdrawal recorded.

Per the European Union (EU) Regulation 536/2014 (Annex V, Point 4) ([17](#)), the following information will be included in Appendix 16.1.13.1 of CTR:

- number of patients included by country
- number of patients inside (member states) and outside the EU (third countries)
- frequency of serious drug-related AEs by treatment, primary system organ class and preferred term.

### **7.8.1 Adverse Events**

AEs will be coded with the most recent version of MedDRA. The version to be used will be specified in RPM and will be displayed as a footnote in the respective output.

The analyses of AEs will be descriptive in nature and will be based on BI standards as presented in “Analysis and Presentation of Adverse Event Data from Clinical Trials – Display Template” [BI-KMED-BDS-HTG-0041] ([8](#)).

The standard AE analyses will be based on the number of patients with AEs (and not on the number of AEs).

The analysis of AEs will be based on the concept of treatment emergent AEs. That means that all AEs will be assigned to ‘screening’ or ‘on treatment’ phases as defined in [Section 6.1](#).

According to ICH E3 ([9](#)), in addition to Deaths and serious adverse events, ‘other significant’ AEs need to be listed in the clinical trial report. These will be any non-serious adverse event

that led to an action taken with study drug (e.g. discontinuation or dose reduced or interrupted).

An overall summary of adverse events (including number of patients with any AE, DLEs, drug related AEs, ocular AEs, AESIs, serious AEs, other significant AEs and drug related serious AEs) will be presented.

The frequency of patients with AEs will be summarised by treatment, primary system organ class (SOC) and preferred term (PT). Separate tables will be provided for patients with serious AEs, for patients with drug-related AEs, for patients with drug-related serious adverse events, for patients with ocular AEs, for patients with DLEs and for patients with AESIs. In addition, the frequency of patients with AEs will be summarised by treatment, worst intensity, primary system organ class (SOC) and preferred term (PT).

The SOCs will be sorted by default alphabetically, PTs will be sorted by frequency (within SOC).

According to the clinical study protocol, adverse events of special interest (AESI) will be analysed:

**Section 5.2.8.1.4 of the CTP:** *The following are considered as AESIs:*

- Hepatic injury  
*A hepatic injury is defined by the following alterations of hepatic laboratory parameters:*
  - *an elevation of AST (Aspartate Aminotransferase) and/or ALT (Alanine Aminotransferase)  $\geq 3$ -fold ULN combined with an elevation of total bilirubin  $\geq 2$ -fold ULN measured in the same blood sample, or*
  - *aminotransferase (ALT, and/or AST) elevations  $\geq 10$  fold ULN*

*These lab findings constitute a hepatic injury alert and the patients showing these lab abnormalities need to be followed up according to the 'DILI checklist' provided in the ISF.*

*In case of clinical symptoms of hepatic injury (icterus, unexplained encephalopathy, unexplained coagulopathy, right upper quadrant abdominal pain, etc.) without lab results (ALT, AST, total bilirubin) available, the Investigator should make sure that these parameters are analysed, if necessary in an unscheduled blood test. Should the results meet the criteria of hepatic injury alert, the procedures described in the DILI checklist should be followed.*

*All AEs meeting the criteria for a dose limiting event (DLE) [...] are defined as AESIs for this trial.*

In addition, non-serious AEs that were reported at a frequency of  $> 5\%$  (at PT level) for patients in at least one treatment group will be summarised by treatment, primary SOC and PT.

For disclosure of adverse events on EudraCT additional information not included in a standard AE analysis will be performed. The following three entries will be created:

- Adverse Events per arm for disclosure on EudraCT
- Non-serious Adverse Events for disclosure on EudraCT
- Serious Adverse Events for disclosure on EudraCT

For all ocular adverse events, ocular symptoms will be listed in addition.

